- If there is any suspicion of NSF

In case of NSF suspicion, a biopsy could be decided by the medical team as a part of the normal patient follow-up in order to confirm or not the diagnosis of NSF. In such a situation, the biopsy results will be collected in a follow-up form.

If any case of suspicion/diagnosis of NSF, the physician in charge of the patient management will promptly inform the local Sponsor (local pharmacovigilance contact) using the dedicated “Suspect Adverse Reaction report” (F006031-See appendix).

Three follow up visits will have to be reported as described below respecting patients' usual follow-up visits:

[figure not shown]
- FUP1: a visit occurring between 3 and 12 months
- FUP2: a visit occurring between 13 and 21 months
- FUP3: a visit occurring between 22 and 27months

Please note that there should be at least 3 months difference between each Follow-up visit reported in order to avoid redundant visits.

If no information could be obtained during the first year after DOTAREM administration from the patient, the physician in charge of the follow-up will be requested to check the hospital/medical notes of the patient and complete a follow up visit form with the data from the hospital notes. This will be requested again during the second year after the DOTAREM administration for the second follow-up and for the last follow-up as well.

The electronic questionnaire for patients of the same centre will be accessible by all investigators of the centre by using personalized logins and passwords. The electronic data collection system also allows follow-up of the changes made by each user.

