- Type of the reaction by reporting a diagnosis or if not available, symptoms
- Date and time to onset of the reaction
- End date of the reaction (will be reported in a follow-up report if the reaction is still ongoing at the time of first notification)
- Name of the drug related to the examination or procedure in cause, date and time of administration, dose administered
- Causal relationship to the drug related to the examination or procedure in cause (mandatory)
- Outcome (no recovery/ recovery / recovery with sequelae/ unknown/death).

Event leading to a SAE report should be reported in the AE section of the case report form.

SAEs should be followed up by the Physician until complete recovery of the patient or, if not possible, until stabilisation of sequelae. The Physician may be requested by the Sponsor to provide follow-up information in order to comply with current regulations as well as for comprehensive assessment purposes.

If a serious event occurs, the Physician is responsible for the measures to be taken to ensure the safety of the study participants.

In addition, if occurring after the end of the patient's follow-up period, SAEs that the Physician thinks may be associated with the study medication/procedure must be reported to the local Sponsor (local pharmacovigilance contact) regardless of the time between the event and the end of the study.

According to local requirements, the Sponsor will communicate relevant safety information to the appropriate agency(ies), International Review Board / Independent Ethics Committee and/or all active investigators, as it becomes available.

The transmission of the information to the Sponsor does not release the Physician from his/her responsibility to inform the regulatory authorities, if applicable.

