1.1. Study objectives

The primary objective of this study is to prospectively estimate the incidence of NSF in patients with moderate to severe renal impairment after administration of DOTAREM®. Patients will be followed during a two-year period after administration of DOTAREM®, to assess if signs or symptoms suggestive of NSF have appeared.

The secondary objectives of the study are:

- to collect a large number of data concerning the general safety profile of DOTAREM® during patient inclusion and MR examination,
- to collect information regarding MRI indication,
- to collect conditions of use/administration of the product in this specific population of patients,
- to collect efficacy data (image and diagnostic quality).

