2.3. Safety criteria

Safety variables collected for this study are:

- Modalities of DOTAREM® administration
 - Volume injected,
 - Type of injection,
 - Number of injections,
 - Nature of package
- From DOTAREM® administration until end of usual follow up in the MR unit
 - Adverse events,
 - Serious adverse events,
 - Adverse events requiring the administration of a concomitant drug,
 - Adverse events according to intensity and outcome,
 - Adverse events related to contrast media injection.
- During the follow-up period

CONFIDENTIAL	FORM STATISTICAL ANALYSIS PLAN N° DGD-55-003 VERSION N° 2 DATED: 26 FEBRUARY 2018 (REF I011622)	F015830-01 Page 9 / 49
--------------	--	---------------------------

- Suspicion of NSF and final diagnosis of NSF,
- Medical events,
- Serum creatinine measurements.

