5.6.2. Primary safety endpoint: NSF

The number and percentage of patients with any suspicion of NSF will be presented.

For patients having any suspicion of NSF, the reasons of the suspicion will be tabulated

Among patient having any suspicion of NSF, the number and percentage of patients with a confirmatory biopsy or not (and the reason if not) will be presented.

Among patients having a confirmatory biopsy, the number and percentage of patients with a final diagnosis of NSF or not (and the reason if not) will be presented.

Listing of NSF suspicion and diagnosis will be presented in CSR appendix 16.2.9.1

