Table 14.3.2.2 Confirmatory Biopsy and Final Diagnosis - Safety Population - Patient with Suspicion of NSF

		Total (N=XXX)
Confirmatory Biopsy	n	xxx
	Yes	xxx (xx.x%)
	No	xxx (xx.x%)
	Missing (if applicable)	xx
If Yes, Final Diagnosis of NSF	n	xxx
	Yes	xxx (xx.x%)
	No	xxx (xx.x%)
	Missing (if applicable)	xx

NSF: Nephrogenic Systemic Fibrosis.

%: (n row / n non missing) * 100, except for Final Diagnosis of NSF %: (n row / n with confirmatory biopsy) * 100.

Source: Listing 16.2.9.1.

Table 14.3.3.1 Overall Safety Summary - Safety Population

	Patients	AEs
At Least One Adverse Event (AE)	xxx (xx.x%)	xxx
Distribution of AE		
- 0	xxx (xx.x%)	-
- 1	xxx (xx.x%)	-
- 2	xxx (xx.x%)	-
- 3 or more	xxx (xx.x%)	-
- Missing (if applicable)	xxx	-
At least one Treatment-Emergent Adverse Event (TEAE)	xxx (xx.x%)	xxx
At least one Serious Adverse Event (SAE)	xxx (xx.x%)	xxx
- Death	xxx (xx.x%)	xxx
- Life-threatening	xxx (xx.x%)	xxx
- Hospitalisation or Prolongation of Hospitalisation	xxx (xx.x%)	xxx
- Persistent or Significant Disability or Incapacity	xxx (xx.x%)	xxx
- Congenital Abnormality or Birth Defect	xxx (xx.x%)	xxx
- Medically Important	xxx (xx.x%)	xxx

CONFIDENTIAL	FORM STATISTICAL ANALYSIS PLAN N° DGD-55-003 VERSION N° 2 DATED: 26 FEBRUARY 2018 (REF I011622)	F015830-01 Page 37 / 49
--------------	---	----------------------------

	Patients	AEs
- Missing (if applicable)	xxx	xxx
Intensity: At Least One AE:		
- Mild	xxx (xx.x%)	xxx
- Moderate	xxx (xx.x%)	xxx
- Severe	xxx (xx.x%)	xxx
- Missing (if applicable)	xxx	xxx
Outcome: At Least One AE:		
- Recovered	xxx (xx.x%)	xxx
- Not yet Recovered	xxx (xx.x%)	xxx
- Unknown	xxx (xx.x%)	xxx
- Missing (if applicable)	xxx	xxx
At Least One AE Requiring an Administration of Concomitant Drug	xxx (xx.x%)	xxx

MedDRA dictionary version 16.0.

%: (n row / N safety population) * 100.

Source: Listing 16.2.7.1.

Table 14.3.3.2 Treatment Emergent Adverse Events - Overall Summary - Safety Population

Same as table 14.3.3.1

Table 14.3.3.3 Pre-injection Adverse Events by Primary System Organ Class and Preferred Term - Safety Population

	Total (N=xxx)
At Least One TEAE	xxx (xx.x%)
SOC 1	xxx (xx.x%)
- PT 1	xxx (xx.x%)
- PT 2	xxx (xx.x%)
...	
SOC 1	xxx (xx.x%)
- PT 1	xxx (xx.x%)
- PT 2	xxx (xx.x%)
...	

TEAE: Treatment Emergent Adverse Event.

MedDRA dictionary version 16.0.

%: (n row / N safety population) * 100.

Source: Listing 16.2.7.1.

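### Final NSF diagnosis is tabulated only for biopsied patients although biopsy is discretionary, so suspected patients without a biopsy have no final NSF status in any planned table

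*SAP*

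**What the plan says.** - **Objective.** SAP 1.1 sets out to "prospectively estimate the incidence of NSF in patients with moderate to severe renal impairment after administration of DOTAREM". SAP 2.3 names two NSF items for the follow-up period: "Suspicion of NSF and final diagnosis of NSF".
- **Analysis.** SAP 5.6.2 works down a nested sequence. First, "The number and percentage of patients with any suspicion of NSF will be presented". Next come the reasons for suspicion. Then, within the suspected, "the number and percentage of patients with a confirmatory biopsy or not (and the reason if not) will be presented". Last, "Among patients having a confirmatory biopsy, the number and percentage of patients with a final diagnosis of NSF" or without one.
- **Table shell.** In SAP 7.2, Table 14.3.2.2 places the diagnosis under the biopsy answer: "If Yes, Final Diagnosis of NSF". Its footnote divides that row by the number biopsied.
- **Biopsy.** Protocol 3.3 makes it optional: on suspicion, "a biopsy could be decided by the medical team as a part of the normal patient follow-up".
- **Reporting.** Protocol 3.3 and 4 ask the physician to report any suspicion or diagnosis of NSF and do not make a biopsy a condition. The general minimum content of a reaction report in Protocol 4 includes "Type of the reaction by reporting a diagnosis or if not available, symptoms". That is a generic item, not an NSF rule.
- **What is absent.** Neither document gives an NSF case definition, an adjudication step, or a rule for a suspected patient without a biopsy. SAP 3.5 plans no replacement of missing data. SAP 3.3 justifies the sample size by an exact 95% interval for a proportion, but 5.6.2 does not call for that interval.

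**The concern.** A discretionary clinical act decides who can receive a final NSF status in the primary-endpoint tables. A patient whose physician diagnoses NSF on clinical grounds, with no biopsy taken, is counted as suspected and then goes no further. A reader who takes the confirmed count from Table 14.3.2.2 and sets it against the safety population will, without being told, place that patient among the non-cases.

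The endpoint is rare and each case carries weight. SAP 4 puts the NSF rate at less than 1% and says recruitment ended short of 1000 patients. A statement that no NSF was seen, or an upper limit attached to a very small count, can turn on how one or two unresolved suspicions are handled. The plan does not say how.

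**Working it through.** **1. Follow one suspected patient through the planned outputs.**

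| Output | Biopsied | Not biopsied |
|---|---|---|
| Table 14.3.2.1, suspicion | counted | counted |
| Table 14.3.2.2, biopsy Yes/No | Yes row | No row |
| Table 14.3.2.2, final diagnosis | Yes, No or Missing | no row |
| Listing 16.2.9.1 | listed | listed, with reason for no biopsy |

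Write N for the safety population, S for suspected, B for biopsied, D for diagnosed among the biopsied, and U for suspected patients without a resolved biopsy result. The plan prints S over recorded answers, B/S (over non-missing biopsy answers) and D/B. It prints neither D/N nor (D + U)/N. If S = 3 and B = 0, the final-diagnosis percentage is 0/0, and the tables give no NSF figure beyond three suspicions.

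**2. Reproduce the plan's precision table (SAP 3.3, N=1000).** The two-sided 95% Clopper–Pearson limits are: lower = Beta(0.025; x, N−x+1), upper = Beta(0.975; x+1, N−x). For x = 0 the lower limit is 0 and the upper is 1 − 0.025^(1/N).

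| x | Computed | SAP 3.3 |
|---|---|---|
| 0 | 0–0.368% | 0.00–0.37% |
| 1 | 0.003–0.556% | 0.00–0.56% |
| 2 | 0.024–0.721% | 0.02–0.72% |
| 5 | 0.163–1.163% | 0.16–1.16% |

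The other four rows also agree to two decimals. No stated figure is wrong.

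**3. Illustrate the gap between confirmed only and confirmed plus unresolved.** The documents give neither U nor the enrolled N. I assume D = 0, U from 0 to 3, and N of 1000 or 500.

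| U counted as NSF | N=1000 | N=500 |
|---|---|---|
| 0 | 0.00–0.37% | 0.00–0.74% |
| 1 | 0.00–0.56% | 0.01–1.11% |
| 2 | 0.02–0.72% | 0.05–1.44% |
| 3 | 0.06–0.87% | 0.12–1.74% |

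**4. Illustrate the chance of a zero count.** Suppose true incidence is p, a share b of true cases is biopsied, biopsy is fully sensitive, and whether a case is biopsied is independent from patient to patient. Then P(0 confirmed) = (1 − pb)^N. With 0 confirmed, the upper limit for true incidence becomes 0.368%/b. Take p = 0.3% and N = 1000; b is assumed.

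| b | P(0 confirmed) | Upper limit if 0 confirmed |
|---|---|---|
| 1 | 5.0% | 0.37% |
| 0.8 | 9.1% | 0.46% |
| 0.5 | 22.3% | 0.74% |
| 0.25 | 47.2% | 1.47% |

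**The case against.** The strongest reply is that nobody disappears. The first output under the primary endpoint is the count of all suspicions in the safety population. An unbiopsied patient is in it, in the biopsy 'No' row, and in Listing 16.2.9.1 with the reason for no biopsy. Because the final-diagnosis percentage is divided by the number biopsied, the shell leaves such patients out of both numerator and denominator and does not itself call them non-cases. Most of the proposed classification can be built from printed cells: biopsy Yes/No/Missing, then diagnosis Yes/No/Missing.

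Much of that stands, and it rules out several readings a reader might infer:

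- *That the patient drops out of the primary result.* The patient leaves only the confirmed-NSF result.
- *That the patient can never become a case.* Listing 16.2.9.1 has a final-diagnosis column with no stated biopsy condition, and NSF might also surface among serious adverse events or follow-up medical events. But no planned table uses the listing column for unbiopsied patients, and nothing ties the event tables to the primary endpoint.
- *That every unbiopsied suspicion is a lost case.* The suspicion items include itching, joint stiffness and muscle weakness, so some suspicions will not be NSF.
- *That the sickest patients are least often biopsied, or that 0 or 1 cases are expected.* The documents say neither. SAP 3.3 assumes 0% to 4%, and SAP 4 says under 1%, which at N=1000 allows nearly 10.

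The reply does not supply a headline definition of NSF. An inconclusive biopsy has no cell, a clinical diagnosis without biopsy has no row, and the reader must choose both numerator and denominator.

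**Conclusion.** The point holds as a gap in the primary-endpoint definition. Final NSF status is conditional on an optional biopsy, its percentage uses the number biopsied, and neither document says how a suspected patient without a biopsy enters the incidence figure named in the objective. Relative to true NSF, a confirmed-only count can therefore be too low.

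The size is unknown. It is zero if every suspected patient was biopsied with a clear result. The intervals for 1 to 3 unresolved cases are illustrations: they assume that count, treat every unresolved suspicion as NSF, and use N=1000, which was not reached, or an assumed 500. The biopsy shares in the last table are also assumed.

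**What to change.** In SAP 5.6.2 and Table 14.3.2.2:

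1. Class every suspected patient as (a) NSF confirmed by biopsy, (b) NSF excluded by biopsy, or (c) unresolved: no biopsy, or biopsy status or result missing or inconclusive.
2. For (c), show the final-diagnosis field already in Listing 16.2.9.1 wherever it is completed. Add the reason for no biopsy as a row, since 5.6.2 promises it but the Table 14.3.2.2 shell omits it.
3. Report NSF over the safety population twice, each with the exact 95% interval of SAP 3.3: (a) alone as the lower figure, and (a) plus (c) as the upper figure. State that the upper figure may include suspicions that are not NSF.

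The cost is a paragraph of SAP text and a few table rows, drawn from fields the plan already lists. No additional biopsy is asked for. The diagnosis on the reaction report should not be relied on unless the SAP first describes how that source is merged with the study data, which it does not do now. The drawback is a less favourable upper figure if any suspicion went without biopsy.

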5.6.3. Adverse Events

Adverse events (AEs) will be coded in system organ classes and preferred terms using MedDRA dictionary v16.0.

Adverse events occurring or worsening after the "Treatment start date" (Date of MRI examination with DOTAREM®) will be considered as **treatment-emergent** adverse events (TEAEs).

An adverse event will be considered **related to** DOTAREM®, if the relationship to the study drug is doubtful, possible, not assessable or missing.

All AEs will be summarized in an incidence table and a specific table will focus on incidence of TEAEs.

Incidence tables will present the number and percent of patients reporting TEAEs, the number and percent of patients reporting serious adverse events (SAEs) and the number and percent of patients reporting related AEs by system organ class and preferred term.

Adverse event listings will be presented in CSR appendix 16.2.7.

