1.2. Study design

DGD-55-003 is a prospective multinational, multicenter, observational Post-Marketing Study (PMS) including longitudinal safety follow-ups. The number of sites and patients will vary from one country to another.

Patients included in the study should have moderate (eGFR of 30-59 ml/min/1.73 m²) to severe (eGFR<30 ml/min/1.73 m²) and end stage (eGFR<15 ml/min/1.73 m²) renal impairment or dialysis and should be scheduled for a contrast-enhanced MRI with DOTAREM®.

After a patient has satisfied all eligibility requirements, he will undergo a MRI examination with a DOTAREM® administration. All patients will be followed up during 2 years after DOTAREM® administration to collect data on any suspected NSF or NSF related symptoms.

The images will be assessed on-site by the same investigator at each participating hospital.

Safety assessments will include adverse events that occurred during the MRI examination or during the time of usual follow-up post DOTAREM® administration.

CONFIDENTIAL	FORM STATISTICAL ANALYSIS PLAN N° DGD-55-003 VERSION N° 2 DATED: 26 FEBRUARY 2018 (REF I011622)	F015830-01 Page 7 / 49
--------------	--	---------------------------

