3.5. Handling of dropouts or missing data

If the start date of an adverse event is missing, then the adverse event occurs after the DOTAREM® injection.

No replacement of missing data is planned in this study.

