6.2.3.3 Displays of Adverse Events

Table 14.3.3.1 Overall Safety Summary - Safety Population

Table 14.3.3.2 Treatment Emergent Adverse Events - Overall Summary - Safety Population

Table 14.3.3.3 Pre-injection Adverse Events by Primary System Organ Class and Preferred Term - Safety Population

Table 14.3.3.4 Treatment Emergent Adverse Events by Primary System Organ Class and Preferred Term - Safety Population

Table 14.3.3.5 Serious Treatment Emergent Adverse Events by Primary System Organ Class and Preferred Term - Safety Population

Table 14.3.3.6 Treatment Emergent Adverse Events with Relationship to DOTAREM® by Primary System Organ Class and Preferred Term - Safety Population

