Radiological Fields or Specialities*		
Neurology		xx (xx.x%)
Cardiology		xx (xx.x%)
Peripheral Vascular		xx (xx.x%)
Musculoskeletal		xx (xx.x%)
Oncology		xx (xx.x%)
Other		xx (xx.x%)
Number of MR Equipment	n	xx
1		xx (xx.x%)
2		xx (xx.x%)
3		xx (xx.x%)
4		xx (xx.x%)
5		xx (xx.x%)
	Missing (if applicable)	xx
Number of MR Examinations/Week	n	xxx
	Mean (SD)	xx.x (xx.x)
	Median	xx
	Min ; Max	xx ; xx
	Missing (if applicable)	xx
Usual Practice in MR Units		
Allergic History Assessment	n	xx
Yes		xx (xx.x%)
No		xx (xx.x%)
	Missing (if applicable)	xx

CONFIDENTIAL	FORM STATISTICAL ANALYSIS PLAN N° DGD-55-003 VERSION N° 2 DATED: 26 FEBRUARY 2018 (REF I011622)	F015830-01 Page 27 / 49
--------------	---	----------------------------

		Total (N=XX)
Creatinine Level Assessment	n	xx
	Yes	xx (xx.x%)
	No	xx (xx.x%)
	Missing (if applicable)	xx
Other Assessment	n	xx
	Yes	xx (xx.x%)
	No	xx (xx.x%)
	Missing (if applicable)	xx
Patient Consent Form Signature	n	xx
	Yes	xx (xx.x%)
	No	xx (xx.x%)
	Missing (if applicable)	xx
Duration of Follow-up After MR Examination	n	xx
	< 30 min	xx (xx.x%)
	Between 30 min and 1 hour	xx (xx.x%)
	> 1 hour	xx (xx.x%)
	Missing (if applicable)	xx

MR: Magnetic Resonance.

%: (n row / n non missing) * 100, except for multiple answers %: (n row / N centre) * 100.

*As multiple radiological fields or specialities are possible, the sum of percentage could be greater than 100.

Source: Listing 16.2.1.3.

Table 14.1.1.5 Magnetic Fields of MR Equipments - All MR Equipments

		Total (N=XX)
Magnetic Fields	1.5	xx (xx.x%)
	3.0	xx (xx.x%)
	Missing (if applicable)	xx

MR: Magnetic Resonance.

%: (n row / N MR equipment) * 100.

Source: Listing 16.2.1.3.

Table 14.1.2.1 Protocol Deviations - All Included Population

		Total (N=XXX)
At Least One Protocol Deviation		xxx (xx.x%)
Protocol Deviation 1		xxx (xx.x%)
...		...
Protocol Deviation n		xxx (xx.x%)

CONFIDENTIAL	FORM STATISTICAL ANALYSIS PLAN N° DGD-55-003 VERSION N° 2 DATED: 26 FEBRUARY 2018 (REF I011622)	F015830-01 Page 28 / 49
--------------	--	----------------------------

%: (n row / N included) * 100.

Source: Listing 16.2.2.1.

Table 14.1.3.1 Analysis Data Populations - All Included Population

	Total (N=XXX)
Safety Population	xxx (xx.x%)
Efficacy Population	xxx (xx.x%)

%: (n row / N included) * 100.

Source: Listing 16.2.3.1.

Table 14.1.4.1.1 Demographic Characteristics - All Included Population

		Total (N=XXX)
Sex	n	XXX

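### SAP 5.6.3 cuts treatment-emergent adverse events at the MRI date, not the injection; on a date-only comparison, same-day post-injection reactions leave the treatment-emergent tables

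*SAP*

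**What the plan says.** SAP 5.6.3 gives the rule: "Adverse events occurring or worsening after the 'Treatment start date' (Date of MRI examination with DOTAREM®) will be considered as" treatment-emergent. The same section plans serious events, and also "the number and percent of patients reporting related AEs by system organ class and preferred term", without limiting either to treatment-emergent events. The titles of Tables 14.3.3.5 and 14.3.3.6 do impose that limit.

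On the collection window, SAP 1.2 states: "Safety assessments will include adverse events that occurred during the MRI examination or during the time of usual follow-up post DOTAREM® administration". SAP 2.3 describes it as "From DOTAREM® administration until end of usual follow up in the MR unit". The shell of Table 14.1.1.4 (SAP 7.2) has a row "Duration of Follow-up After MR Examination" with three categories: under 30 minutes, "Between 30 min and 1 hour", and over 1 hour.

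Two other places cut at the injection. SAP 3.5 says: "If the start date of an adverse event is missing, then the adverse event occurs after the DOTAREM® injection". SAP 6.2.3.3 titles Table 14.3.3.3 "Pre-injection Adverse Events by Primary System Organ Class and Preferred Term - Safety Population", but the SAP gives no inclusion rule for that table.

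**The concern.** The contrast agent is given at the MRI visit, and observation in the MR unit is counted in minutes or hours. The reactions that this window is meant to catch should therefore mostly begin on the MRI date, and a rule requiring onset after that date sets them aside. The general safety profile is the first secondary objective in SAP 1.1, and the treatment-emergent tables are where a reader will look for it.

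Two programmers could obtain different treatment-emergent rates from the same data, and the literal reading gives the lower ones. Because the rule for Table 14.3.3.3 is undefined, a reaction that followed the injection could also be reported there as having preceded it.

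**Working it through.** The plan states no figure that depends on this rule, so there is none to reproduce. The check compares the sections and applies the possible rules to example times.

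**1. Where onsets fall.** Collection runs from injection to the end of usual follow-up in the MR unit (SAP 2.3), with categories from under 30 minutes to over 1 hour (shell of Table 14.1.1.4). Most onsets should be on the MRI date.

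**2. What each reading does.** Assume the MRI starts at 10:00 and the injection is at 10:30. The entries show whether an event counts as treatment-emergent.

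| Onset | AE date > MRI date | AE date ≥ MRI date | AE date-time > MRI date-time | AE date-time ≥ injection |
|---|---|---|---|---|
| 09:50, before the MRI | no | yes | no | no |
| 10:10, in the scanner before injection | no | yes | yes | no |
| 10:40, after injection | no | yes | yes | yes |
| 09:00 next day | yes | yes | yes | yes |

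The first column is 5.6.3 taken at its word with dates only. It misses the 10:40 reaction. The second keeps it but also counts both pre-injection events. The third keeps it and still counts the 10:10 event. Only the last separates before from after injection. The 10:10 event is within scope, because SAP 1.2 includes events during the examination.

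**3. What time resolution is available.** Listing 16.2.7.1, named as the source in the adverse-event table shells, shows onset and MRI as dates only. The shells of the death and serious-event listings (Tables 14.3.3.7 and 14.3.3.8) show hours and minutes for both. Times may therefore exist, but the SAP does not say that the rule uses them.

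**4. Which tables are affected.** SAP 6.2.3.3 lists six summary tables, 14.3.3.1 to 14.3.3.6.
- If the 5.6.3 text governs the serious and related tables: 14.3.3.2 and 14.3.3.4, so 2 of 6.
- If the table titles govern: also 14.3.3.5 and 14.3.3.6, so 2 + 2 = 4 of 6.
- In both cases the treatment-emergent row of 14.3.3.1 is affected as well.

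**5. Consistency with the injection-based cuts.** Under SAP 3.5 an undated event is placed after the injection and would presumably count as treatment-emergent; an event dated to the MRI day would not. If Table 14.3.3.3 is programmed as everything that is not treatment-emergent, same-day reactions are labelled pre-injection. If it is programmed as onset before injection, they fall in neither Table 14.3.3.3 nor Table 14.3.3.4.

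**The case against.** The strongest reply is that the intention is clear. Collection starts at the injection, undated events are placed after it, and a pre-injection table sits beside the treatment-emergent one. A rule that excluded nearly every reaction the study collects is unlikely to be what the authors meant. The hours and minutes in the death and serious-event shells also point to a date-time comparison, which would keep same-day reactions.

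Much of this stands: it is probably a drafting defect, and the loss is not certain to occur. It does not remove the problem. The natural repairs classify events differently (step 2), and a date-time comparison with the MRI still counts events between the start of the examination and the injection.

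Three stronger readings are tempting and are not supported:
- A reader might infer that same-day reactions disappear from the report. They do not: the all-event rows of Table 14.3.3.1 and Listing 16.2.7.1 keep them, and SAP 5.6.4 lists all deaths and serious events.
- A reader might infer that they appear in no table by system organ class and preferred term. That needs Table 14.3.3.3 to be cut at injection and the titles of 14.3.3.5 and 14.3.3.6 to govern. If the 5.6.3 text governs, serious and related same-day reactions are still tabulated, and 5.6.3 defines related broadly (doubtful, possible, not assessable or missing).
- A reader might apply the 0.4% event rate from Protocol section 1 to 1,000 patients. That rate is per examination in another population, SAP 3.3 says 1,000 was not reached, and the documents give no share of events starting on the MRI date. Nor need every event fall on that date: Protocol section 4 has events that lead to a serious-event report entered in the adverse-event section, and asks for reports of suspected NSF over the two-year follow-up.

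**Conclusion.** The point holds as a defect in a stated rule. Followed with a date-only comparison, SAP 5.6.3 excludes same-day post-injection reactions from 2 of the 6 summary tables, or 4 of 6 if the titles govern, plus one row of Table 14.3.3.1. It also conflicts with the injection-based cuts in SAP 3.5 and in the title of Table 14.3.3.3. This rests on two assumptions: that most events start on the MRI date, which follows from the collection window, and that dates are compared without times, which the SAP leaves open. The number of patients affected cannot be derived, because neither onset times nor the final sample size is given. The primary NSF tables do not use the rule, and all statistics are descriptive. It should be corrected, but it does not threaten the primary result.

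**What to change.** In SAP 5.6.3:
- Define a treatment-emergent event as one with onset or worsening at or after the DOTAREM injection, using date and time where recorded.
- Count same-day events of unknown time as treatment-emergent unless they are recorded as pre-injection, in line with SAP 3.5.
- Define Table 14.3.3.3 as onset before injection.
- State whether the serious and related tables are limited to treatment-emergent events, and make the titles of 14.3.3.5 and 14.3.3.6 agree with the text.

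The cost is a few sentences and possibly two table titles, with no new data. For serious events, Protocol section 4 already asks for the times of onset and administration. Treatment-emergent rates may become slightly less favourable, and a few same-day pre-injection events of unknown time may be counted as treatment-emergent.
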